7.3. Missing Data

For participants who are withdrawn from the study prior to the end of the study, all data collected up to the point of discontinuation will be used for analysis. There will be no imputation for missing data, unless otherwise specified.

7.4. Visit Windows

If there are multiple planned assessments for any study procedure at a given time point the latest non-missing value will be used for summarization, unless specified otherwise. Unscheduled assessments will be listed and will be used to flag baseline visit if this is the last non-missing assessment before the first dose of study drug, but unscheduled assessments will not be included in the summarization.

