8.2.3.1. Safety Review of 12-lead Electrocardiograms

All recorded ECGs will be reviewed by the Investigator or qualified designee. If a participant shows an abnormal ECG, additional safety recordings (including the use of 5- or 12-lead Holter equipment) may be made, and the abnormality will be followed to resolution.

8.2.3.2. 24-hour Holter Electrocardiograms/Real Time Display (Cardiac Telemetry)

Holter recording will be performed up to 3 months prior to Day 1, and telemetry will be used on dosing days as specified in Section 1.3. Electrocardiogram telemetry will be monitored by the Investigator or qualified member of clinical staff. This will allow the extraction of 10-second 12-lead ECG data files, which can be transferred onto the MUSE. All ECG files so acquired will then be analyzed and over-read using the same process as for any other 12-lead ECG. The ECG Holter/telemetry reports will be archived with study documents.

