7.2. Key Definitions

End of Study (EOS)

The EOS for each participant is defined as the date the participant completes the last visit or date of discontinuation. EOS for each individual participant is anticipated to be Day 127 and Day 155 for single ascending dose (SAD) and multiple ascending dose (MAD) cohorts, respectively, or the time point at which complement activity has normalized, if later than Day 127 or Day 155.

This document is confidential.

Trial day

If the event date \geq date of first dose of investigational product (IP), trial day = event date – date of first dose of IP + 1.

If the event date < date of first dose of IP, trial day = event date – date of first dose of IP.

Nominal Time

Nominal time is the scheduled measurement time relative to time 0. Time 0 is the time of study drug dosing on Day 1.

Baseline Value

Baseline is defined as the last non-missing assessment (including repeated and unscheduled assessments) prior to treatment on Day 1, unless otherwise specified.

Change from Baseline (CFB)

CFB = Post-baseline value – Value at baseline

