All summaries will be based on results in SI (standard international system of units) units and will be output in the order listed above.

Toxicity grading following the NCI CTCAE grades version 5.0 will also be derived for laboratory variables where applicable (see list below). Note, where gradings require investigator/clinical input, this will not be considered and only the numeric criteria will be used for the assignments. If this results in the criteria for more than one grade being met, the highest (worst) CTCAE grade will be assigned. For creatinine only, the criteria based on the upper limit of normal (ULN) will be used (changes compared to the baseline value will not be used), e.g., CTCAE defines Grade 1 as $> \text{ULN} - 1.5 \times \text{ULN}$ or $> 1 - 1.5 \times \text{baseline}$. Only the $\text{ULN} - 1.5 \times \text{ULN}$ criterion will be used (and not the baseline criterion).

This document is confidential.

The following parameters are CTCAE gradable:

- **Hematology:** Absolute neutrophil count (neutrophil), total leukocytes (Leukocytes), hemoglobin (only do the grading for Anemia, no grading for Hemoglobin increased), platelet count, Lymphocyte.
- **Coagulation:** International normalized ratio.
- **Chemistry:** Alanine aminotransferase albumin, alkaline phosphatase, aspartate aminotransferase, total bilirubin, creatinine, gamma-glutamyl transferase, glucose (only do the grading the Hypoglycemia, no grading for Hyperglycemia), creatine kinase.

Actual values and changes from baseline (screening) in hematology, coagulation, clinical chemistry, and urinalysis will be summarized by treatment.

Shift tables for hematology, clinical chemistry and coagulation from baseline CTCAE toxicity for each visit and to the maximum CTCAE grade on treatment for each parameter will be provided. Participants with both a non-missing baseline and at least one non-missing post-baseline grade will be included in the shift tables. Unscheduled data will be included in the worst case across all scheduled and unscheduled visits after the first dose of study treatment. This means that if there are CTCAE grades derived from both unscheduled and scheduled visits data per test per participant then the highest grade will be summarized.

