11.4. ECG

The ECG parameters include heart rate, PR, RR, QRS, QT, and corrected QTcF intervals.

Analysis of drug related QT/QTc interval changes relative to serum PK concentrations will be conducted on all dose regimens. The principles of this analysis follow the statistical methods described by Garnett et al. (Garnett, 2018). All ECG recordings will be in triplicate and compliant with the correct recording and manual adjudication of ECG in thorough QT/QTc studies. The ECG analyses will be based on adjudicated selected triplicates from each time point. The average of the triplicate ECG readings at the time points collected will be calculated, and changes from pretreatment baseline values will be assessed by each cohort. The average of the triplicate ECG readings will be used to derive QT/QTc at all visits (*i.e.* both pre- and post-baseline visits). An outlier analysis will be performed that will summarize the absolute count, frequency and percentage of participants who meet any of the following outlier criteria at each visit by cohort:

- QT, QTcF interval > 450 msec
- QT, QTcF interval > 480 msec
- QT, QTcF interval > 500 msec
- QT, QTcF interval increases from baseline > 30 msec

This document is confidential.

- QT, QTcF interval increases from baseline > 60 msec

Actual values and change from baseline of these average ECGs will be summarized by treatment.

All ECG parameters, including all single ECG measurements, but also the mean value and overall ECG evaluation will be provided in data listings.

If a participant shows an abnormal ECG, additional safety recordings (including the use of 5- or 12-lead Holter equipment) may be made, and the abnormality will be followed to resolution. The 24-hour Holter ECG recording results will be provided in data listings.

If deemed necessary, a separate concentration-QT analysis may be performed by Alexion. The concentration-QT analysis is not within the scope of this SAP.

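### The QT/QTcF outlier table omits a participant who crosses a threshold only on an unscheduled post-dose ECG, and never shows how many participants had at least one outlier

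*SAP*

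**What the plan says.** **General rule.** SAP section 7.4 (Visit Windows) lists unscheduled assessments, "but unscheduled assessments will not be included in the summarization". The sentence before it, on multiple planned assessments, allows for exceptions specified elsewhere. This one does not.

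**Baseline.** SAP section 7.2 lets unscheduled pre-dose values define baseline: "Baseline is defined as the last non-missing assessment (including repeated and unscheduled assessments) prior to treatment on Day 1".

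**ECG.** SAP section 11.4 summarises "participants who meet any of the following outlier criteria at each visit by cohort". The criteria are QT or QTcF above 450, 480 and 500 msec, and increases from baseline above 30 and 60 msec. No row covers the whole post-baseline period, and unscheduled ECGs have no rule of their own. On the data to be used, it says: "The ECG analyses will be based on adjudicated selected triplicates from each time point". Triplicates are averaged. All single measurements and Holter results go into listings.

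**Extra recordings are foreseen.** Protocol section 8.2.3.1 says: "If a participant shows an abnormal ECG, additional safety recordings (including the use of 5- or 12-lead Holter equipment) may be made". SAP section 11.4 repeats this.

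**Laboratory data.** For the toxicity-grade shift tables, SAP section 11.2 says: "Unscheduled data will be included in the worst case across all scheduled and unscheduled visits after the first dose of study treatment". The normal-range shift tables have a similar worst-case row.

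**Protocol.** Section 9.4.2.1 also counts QT outliers by visit, by cohort and treatment arm. It is silent on unscheduled ECGs.

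**The concern.** ECG results are part of the primary safety endpoint, and the outlier table is the plan's categorical summary of QT. A reader will take a zero in the row for "QT, QTcF interval > 500 msec" to mean that nobody reached that value. Under the rules as written it means only that nobody reached it on an averaged triplicate at a scheduled visit.

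The plan expects extra recordings after an abnormal ECG, so unscheduled ECGs are foreseeable, and leaving them out can only lower the count of affected participants or leave it unchanged. The plan is also uneven. An unscheduled pre-dose ECG can set the baseline, but an unscheduled post-dose ECG cannot count as an outlier. Unscheduled laboratory values count in the worst-case rows, but unscheduled ECGs have no such row.

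The second problem does not depend on unscheduled data. Visit rows cannot be added up, because the same participant may appear in several of them.

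**Working it through.** The plan states no figure on this point, so there is none to reproduce. The check is a reading of the rules, followed by arithmetic for scale.

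**1. Which ECGs reach the outlier table**

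| Situation, for a given criterion | Counted? | Source |
|---|---|---|
| Averaged triplicate at a scheduled visit exceeds the limit | Yes, at that visit | SAP 11.4 |
| Scheduled ECG is abnormal but within the limit; an unscheduled repeat exceeds it | No | SAP 7.4, with no exception in 11.4 |
| An unscheduled ECG between visits exceeds the limit; no scheduled ECG does | No | SAP 7.4, with no exception in 11.4 |

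This applies criterion by criterion. A participant counted above 450 msec at a visit is still missing from the 500 msec row if that limit was passed only on an unscheduled ECG.

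**2. Could an unscheduled ECG be the only record?**

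The longest gaps between scheduled triplicate ECGs, from the Protocol's schedules of activities, are:

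- Single-dose cohorts (Table 5): Day 29 to 57, 71 to 99 and 99 to 127, for example 57 − 29 = 28 days.
- Cohorts 8 and 9 (Table 8): Day 71 to 99, 99 to 127 and 127 to 155, each 28 days.
- Cohort 10 (Table 11): Day 22 to 57, or 57 − 22 = 35 days.

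So it could, mainly in later follow-up. Around the first and last doses the scheduled ECGs are dense.

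**3. Scale**

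Inputs: 6 active participants per cohort and 60 in total (SAP section 4.1). Assumption: exactly one active participant passes 500 msec, and only on an unscheduled triplicate. Limits are exact (Clopper-Pearson) 95%. For 0/n the upper limit is 1 − 0.025^(1/n). For 1/n the lower limit is 1 − 0.975^(1/n), and the upper limit is the 97.5% point of a Beta(2, n − 1) distribution.

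| | As planned | With an any-time row |
|---|---|---|
| Cohort | 0/6 = 0% (0 to 45.9%) | 1/6 = 16.7% (0.4 to 64.1%) |
| All active | 0/60 = 0% (0 to 6.0%) | 1/60 = 1.7% (0.04 to 8.9%) |

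If optional Cohort 7 is not opened, the total is 60 − 6 = 54 and the all-active figure is 1/54 = 1.9%.

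**4. Visit rows and participants**

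Suppose a cohort shows one outlier at Day 8 and one at Day 15. That may be one participant (1/6 = 16.7%) or two (2/6 = 33.3%). The table cannot tell these apart.

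**The case against.** Most of the case on the other side concerns how far the point reaches.

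- **Crossings at scheduled visits are already counted.** If the abnormal ECG that prompted extra recordings was scheduled and over the limit, the participant is in the table. A reader might infer that any QTcF above 500 msec found in follow-up is lost. It is not, because ECGs at scheduled follow-up visits count. This stands, and it limits the point to crossings seen only on unscheduled ECGs.
- **Selective loss is not shown.** A reader might infer that the dropped recordings are those most likely to hold the worst value. The documents do not support that. Extra recordings follow an abnormality until it resolves, so they may equally show recovery.
- **The data are reported elsewhere.** Unscheduled ECGs are listed, and clinically significant abnormalities meet the adverse event definition. The QT stopping rules use uncorrected QT and do not depend on this table. With six active participants per cohort and descriptive analysis only, listings are practical to read. This lowers the stakes, but it does not correct a summary row that shows zero.
- **The laboratory comparison is imperfect.** Laboratory values need no averaging or adjudication. Extra ECG recordings may be Holter or single tracings, and neither document says how these become averaged triplicates, although both say all ECG recordings will be in triplicate. This stands and shapes the fix.
- **Details may sit elsewhere.** The Protocol allows a separate ECG analysis plan, and SAP section 7.1 refers to table shells. Either might already contain an any-time row. Neither is available here.

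**Conclusion.** The point holds in a limited form. With SAP sections 7.4 and 11.4 followed as written, a participant who crosses a QT or QTcF limit only on an unscheduled post-dose ECG is absent from the outlier table. The number of participants with at least one outlier is never shown, whether or not any ECG is unscheduled.

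The exclusion is not universal. Baseline selection and the laboratory worst-case shift rows use unscheduled values, while by-visit laboratory summaries still fall under section 7.4. Nor is any value lost from the record.

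The figures of 16.7% for a cohort and 1.7% for all active participants illustrate a single missed participant. They are not estimates, because the documents give no expected rate of unscheduled ECGs or of threshold crossings. The conclusion assumes that no table shell or separate ECG plan already adds the row. The change is worth making because it is cheap and concerns a primary safety summary.

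**What to change.** In SAP section 11.4:

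1. For each criterion (above 450, 480 and 500 msec; increase above 30 and 60 msec), add a row *any time post-baseline, scheduled and unscheduled*. Count each participant once at the worst value, by cohort and treatment arm.
2. Keep the by-visit rows on scheduled data.
3. Limit the new row to averaged, adjudicated triplicate 12-lead ECGs. Footnote or list separately any unscheduled single, unadjudicated or Holter reading that crosses a limit.

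In SAP section 7.4, cross-refer to this row as an exception.

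The rule need not extend to vital signs: SAP section 11.3 plans only actual values and changes from baseline, so no categorical summary exists to change.

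The cost is a few sentences and one row per criterion. Counts may be slightly less favourable, and participants with more recordings have more chances to cross a limit. A footnote giving the number of participants with unscheduled ECGs would help the reader allow for that.

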7.5. Pooling of Centers

Not Applicable.

7.6. Subgroups

Not Applicable.

This document is confidential.

8. Participant Disposition, Demographic, Other Baseline Characteristics and Medication

8.1. Participant Disposition and Withdrawals

Listings of treatment assignments, including the participant's identification and date of randomization will be presented.

The following frequencies (number and percent) will be displayed for all screened participants: participants randomized, screen failures with reasons and COVID-19 related reasons for screen failure.

The analysis sets will be summarized with counts and percentages by cohort and study intervention within each cohort and overall. This table will include the following: number of participants in the Enrolled Set, number of participants in the Safety Set, reasons for exclusion from the Safety Set, number of participants in the PK/PD sets, reasons for exclusion from the PK/PD sets, number of participants in the Immunogenicity Set and reasons for exclusion from the Immunogenicity Set.

The frequencies, number and percent, will be displayed for all participants in the Enrolled Set: participants who received treatment for each cohort, participants who completed the study, participants who discontinued early, participants who discontinued due to COVID-19 and study duration in days. The denominators will be the number of enrolled participants.

The number and percent of participants who discontinued early will also be presented by reason for early discontinuation, also for all participants combined. The denominators will be the number of participants who received the treatments.

Completion/discontinuation status, inclusion/exclusion criteria definitions and inclusion/exclusion criteria violations will be listed by participant.

A listing of participants excluded from the analysis sets will also be generated.

8.2. Protocol Deviations

Protocol deviation management at Syneos Health is detailed in Protocol Deviation and Non-compliance Management (3101.W02). For details on the process for defining analysis datasets refer to (Blind) Data Review and Definition of Analysis Sets SOP (3911).

All protocol deviations recorded in Clinical Trial Management System (CTMS) will be listed. The Protocol deviation criteria are graded as not important or important. Important protocol deviations and important protocol deviations related to COVID-19 will be summarized by the number and percentage of participants for the Safety Set.

8.3. Demographic and Baseline Characteristics

Demographic and baseline characteristics, including sex, female child-bearing potential, race, ethnicity, Japanese Descent, age, height, body weight, and body mass index (BMI) will be summarized on the Safety Set using standard descriptive statistics. No formal statistical comparisons between populations will be performed. Demographics and informed consent data will be listed for all participants in the Enrolled Set.

Height (in cm) = height (in inches) * 2.54

This document is confidential.

Weight (in kg) = weight (in lbs) * 0.4536

BMI (kg/m²) = Weight(kg)/[Height(m)²]

8.4. Medical History and Concomitant Diseases

Medical history will be coded using MedDRA version 23.1 and summarized for the Safety Set, presenting the number and percentages of participants within each preferred term (PT) grouped by the system organ class (SOC). A participant with multiple occurrences of an event in a PT is counted only once. Medical history will be listed by participant.

8.5. Medication

The WHO Drug Dictionary, WhoDrugGlobalB3 Sep 2020, will be used to classify prior and concomitant medications by therapeutic class and drug name.

Prior medication is defined as any medication taken before the date of the first dose of study treatment. Concomitant medication is defined as any medication taken on or after the date of the first dose of study treatment.

The use of prior and concomitant medications will be summarized by the number and percentage of participants for the Safety Set. If a participant took a specific medication multiple times or took multiple medications within a specific therapeutic class, that participant would be counted only once for the coded drug name or therapeutic class.

Tetravalent Meningococcal Conjugate Vaccine (MCV4) and Meningococcal Serogroup B immunization results will be summarized for the Safety Set, presenting the number and percentages of participants who received the MCV4 and Meningococcal Serogroup B immunizations by timing (*i.e.* prior to consent or after consent). MCV4 and Meningococcal Serogroup B immunization results will be listed by participant.

8.6. Extent of Exposure

Exposure data will be summarized by total dose administered (mg), total volume administered (mL) and the number of interruptions (SC Infusion/IV) by cohort. Exposure will be listed by participant.

8.7. Treatment Compliance

Compliance of IP (%) intake will be calculated as follows:

- (Total dose (mg) that the participant actually received and took / total expected dose (mg) that the participant was meant to receive) x 100

This document is confidential.

9. Pharmacokinetics

Pharmacokinetic analyses will be performed using the PK Set and will be reported by cohort.

PK parameters will be calculated using noncompartmental methods with Phoenix® WinNonlin® (Certara USA Inc., Princeton, New Jersey) Version 8.0 or higher. Calculations of individual PK parameters will be based on individual serum concentration data from participants who receive ALXN1820 SC or ALXN1820 IV with actual sampling dates and times.

9.1. PK/PD Sampling Schedule

Whole blood samples for PK analysis and pharmacodynamic (PD)/ biomarkers will be collected at various different timepoints for different cohorts. The timing of sampling may be altered during the course of the study based on newly available data to ensure appropriate monitoring.

9.2. Serum PK Endpoint

The following PK parameters will be derived from the serum concentrations of ALXN1820:

For the single dose cohorts 1-7, PK parameters will be derived on Day 1.

For the multiple dose cohort 8, PK parameters will be derived on Day 1 and 29.

For the multiple dose cohorts 8 and 9, PK parameters will also be derived on Day 8, 15 and 22 (when possible using limited sampling schedule up to 24h*).

For the multiple dose cohort 10, PK parameters will be derived on Day 1, 8 (when possible using limited sampling schedule up to 24h*) and 15.

* Only selected PK parameters might be derived due to limited sampling up to 24 h such as C_{max} , t_{max} , and AUC_{0-24} etc.

Refer to Section 1.3 of the Protocol for the full sample schedule.

Parameters	Dosing	Definition
C_{max}	SD, MD	Maximum observed serum concentration
t_{max}	SD, MD	Time to maximum observed serum concentration
[name]	Area under the serum concentration versus time curve from time 0 to the last quantifiable concentration
AUC_{tau}	MD	Area under the concentration-time curve during the dosing interval
$AUC_{0-\infty}$	SD, MD	Area under the concentration-time curve from time 0 (dosing) to time infinity
$t_{1/2}$	SD, MD	Terminal elimination half-life
λ_z	SD, MD	Terminal-phase elimination rate constant
CL or CL/F	SD, MD	Total body clearance or apparent clearance
V_d or V_d/F	SD, MD	Volume of distribution or apparent volume of distribution
F	SD	Absolute bioavailability
R_{ac}	MD	Accumulation Ratio

Abbreviations: MD = Multiple-dose; SD = Single dose

This document is confidential.

Note: tau is the dosing interval for steady-state data, *i.e.*, the time between doses (tau = 1 week).

The absolute bioavailability for the ALXN1820 SC cohorts will be defined by the ratio of the geometric means for the AUC_{0-∞} parameter for the ALXN1820 SC cohort over the ALXN1820 IV cohort. For the absolute bioavailability estimates, a 95% CI for each of the ratio of the geometric means will be provided.

The primary PK parameters will be summarized by overall treatment and the sub treatment category ADA status (at least one positive/negative). Boxplots will present PK levels by ADA status and by healthy non-Japanese participants and participants of Japanese descent. Some PK parameters may not be calculated for all or some subjects, at the discretion of the pharmacokineticist, if the concentration data are not deemed to be amenable to evaluation. Explanations for PK parameters that could not be estimated will be provided in the report.

